**-Standardized ultra-conservative Or Physician-directed ICD programming for SHOCK reduction among patients on continuous flow LVAD support: a randomized controlled trial (STOP SHOCK LVAD study)**

Study Design	Randomized unblinded clinical trial
Planned Number of Patients	280 patients; 140 per treatment arm
Randomization Method	REDCap
Treatment Arms	A) Ultraconservative ICD programming for maximal shock avoidance (see table at end of protocol)  B) Physician Discretion
Primary Endpoints	Any ICD shock Mortality Syncope
Secondary Endpoints	Time to first ICD shock Time to first ICD shock for VT/VF Quality of Life questionnaire Hospitalizations; including HF and ventricular arrhythmia
Inclusion Criteria	
 
- >18 years of age
 
- Pre-existing ICD
 

Exclusion Criteria	
 
- Non-functional ICD system
 
- Uncontrolled ventricular arrhythmias <math>\leq 7</math> days of enrollment (defined as VT/VF >30 seconds and/or causing hemodynamic instability and/or symptoms or pre-syncope or syncope)
 

Follow-up schedule	Routine post-LVAD care; no additional study visits  Remote ICD monitoring encouraged
Study Duration	2 years

## **INTRODUCTION**

The proposed study will evaluate the utilization of an ultra-conservative programming strategy to reduce shocks for ventricular arrhythmias (VA) in heart failure (HF) patients with an implantable cardioverter-defibrillator (ICD) and a continuous-flow (CF) left ventricular assist device (LVAD). The survival benefit of ICDs with VA detections and therapies enabled has been established in HF patients with reduced ejection fraction (EF) without LVAD, as well as HF patients with older-generation, pulsatile-flow (PF) LVADs. However, newer studies do not demonstrate the same benefit of VA tachy-therapy in patients with current-generation CF LVAD devices, potentially due to better hemodynamic tolerability of VA. In addition, ICD shocks are known to worsen clinical outcomes while causing patients psychosocial harm. Recent studies have applied extended-detection programming to successfully reduce ICD shocks in non-LVAD HF patients. However, shock reduction strategies have not been previously evaluated in LVAD patients in an adequately-powered, randomized clinical trial. This study will prospectively randomize HF patients with pre-existing ICDs to programming at the discretion of their EP provider versus “ultra-conservative” ICD programming, in which a single ventricular fibrillation (VF) zone will be programmed using the maximum rate cutoff allowable across all ICD manufacturers (250 beats per minute [bpm]), as well as the manufacturer-specific maximum detection intervals. In the ultra-conservative arm, a monitor-only zone will be programmed at 150 bpm. The primary endpoint will be the percentage of patients receiving an ICD shock at 2-year follow-up with planned interim analyses at 6 months and 1 year. Secondary endpoints include time to first ICD shock, time to first VT/VF shock, and Quality Life questionnaires. Data collected will include mortality, syncope, LVAD-related hospitalizations (including HF, VA), and the percentage of patients receiving inappropriate ICD shocks at 2-year follow-up. The study hypothesis is that the standardized application of ultra-conservative ICD programming will reduce shocks and improve quality of life without an increase in mortality, syncope, or hospitalizations compared to physician discretion programming in CF LVAD patients.

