## **OBJECTIVES AND ENDPOINTS**

To evaluate the utilization of an “ultra-conservative,” single-zone programming strategy for ICD tachy-therapies in CF LVAD patients as compared to a passive strategy of standard programming (at the discretion of the provider). The study hypothesis is that an ultra-conservative strategy will result in a reduction in shocks and an improvement in quality of life without increasing adverse outcomes including death, hospitalization, and syncope among patients on CF LVAD support.

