### *Sample Size*

The projected sample size is 280 enrolled subjects, 140 randomized to each programming arm. Prior observed ICD shock rates in similar CF LVAD + ICD cohorts were 21% over 11 month follow-up in a study by Richardson et al [27] and 13% over 15 month follow-up in the aforementioned internal study currently under review by Kiehl et al. We thus projected an annual ICD shock incidence of 17% (the mean of the prior 2 studies). Thus, in order to detect a 15% absolute risk reduction in shocks over 2-year follow-up with 80% power and two-tailed  $\alpha=0.05$ , 280 patients are needed.

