### *Statistical Plan*

At the end of study enrollment, baseline characteristics will be compared with potential covariates of interest able to later be balanced either via multi-variable regression or propensity analysis if needed. For continuous outcomes, linear regression will be utilized, for categorical outcomes, logistic regression will be utilized, and for time to event outcomes, Cox regression will be utilized.

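### The hypothesis claims no increase in mortality, syncope or hospitalizations, but the trial is sized for shocks alone and sets no criterion that could support that claim

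*Combined protocol and SAP*

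**What the plan says.** The study hypothesis appears twice, each time with a benefit part and a no-harm part. The Introduction expects the strategy to "reduce shocks and improve quality of life without an increase in mortality, syncope, or hospitalizations compared to physician discretion programming". Objectives and Endpoints expects fewer shocks and better quality of life "without increasing adverse outcomes including death, hospitalization, and syncope among patients on CF LVAD support".

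The only sample-size calculation concerns shocks: "The projected sample size is 280 enrolled subjects, 140 randomized to each programming arm", chosen "in order to detect a 15% absolute risk reduction in shocks over 2-year follow-up with 80% power". It gives no expected rate, tolerable excess or power for death, syncope or hospitalization.

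The Statistical Plan assigns methods by type of outcome: linear regression for continuous outcomes, and "for categorical outcomes, logistic regression will be utilized, and for time to event outcomes, Cox regression will be utilized". It does not say what result would support the no-harm part. Data Monitoring gives adverse-event review to the principal investigator and states no harm criterion.

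The documents also disagree on the standing of the safety outcomes. The synopsis table lists mortality and syncope with any ICD shock as primary endpoints. The Introduction names shock alone as primary and places mortality and syncope among the data to be collected.

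**The concern.** A trial sized to detect a difference in one outcome does not, by failing to find a difference in another, show that the other is unchanged. Half of this hypothesis is a claim of no increase, and the plan does not say how it would be established. That leaves room for a non-significant mortality or syncope comparison to be taken as confirmation, even when the data are compatible with a sizeable excess.

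Safety is central to this question. The ultra-conservative arm starts with VT detection and therapy off and device therapy from 250 bpm. The Study Rationale says that arrhythmias in this population usually exceed 200 bpm, and that guidelines recommend re-activating tachy-therapy. Readers of a positive shock result will look next to the safety statement.

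**Working it through.** **Inputs from the documents.** 140 per arm; 17% annual shock incidence; 15-point absolute reduction over 2 years; 80% power; two-sided 0.05 (all from Sample Size).

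**Inputs assumed.** 2-year control mortality of 10%, 20% or 30%; syncope of 5%; a true mortality excess of 8 points, chosen only as an illustration; known 24-month status for every patient.

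**1. The plan's own figure.** The 2-year control shock rate is not stated. Doubling 17% gives 34%, and compounding gives 1 − 0.83² = 31.1%.
- 34% v 19%: the pooled two-proportion formula needs 135 per arm (270 in total). Power at 140 per arm is 81.5%.
- 31.1% v 16.1%: the continuity-corrected formula needs 138 per arm (276). Power at 140 per arm, uncorrected, is 84.4%.
- A Freedman log-rank calculation for 34% v 19% gives exactly 280.

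The variant used is not stated, but 280 is a reasonable size for the shock claim.

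**2. Precision for safety outcomes.** With equal true rates p, SE = √(2p(1−p)/140) and the 95% half-width is 1.96 × SE.

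| Assumed p | SE | Half-width (points) |
|---|---|---|
| 5% (syncope) | 0.0260 | 5.1 |
| 10% | 0.0359 | 7.0 |
| 20% | 0.0478 | 9.4 |
| 30% | 0.0548 | 10.7 |

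**3. Chance of missing an 8-point excess of deaths.** Let p̄ be the mean of the two rates. Power = Φ{[d − 1.96√(2p̄(1−p̄)/n)] / √[(p₁(1−p₁)+p₂(1−p₂))/n]}, with d = 0.08 and n = 140.
- 10% v 18%: (0.08 − 0.0813)/0.0412 = −0.03; power 0.49, so non-significant 51% of the time.
- 20% v 28%: (0.08 − 0.1000)/0.0508 = −0.39; power 0.35, non-significant 65%.
- 30% v 38%: (0.08 − 0.1110)/0.0564 = −0.55; power 0.29, non-significant 71%.

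**4. An example result.** Take 42 v 28 deaths, which is 30% v 20%. The pooled test gives z = 0.10/√(2 × 0.25 × 0.75/140) = 1.93, p = 0.053. The 95% CI is 10 ± 1.96 × 5.14, or −0.1 to +20.1 points. This is non-significant, yet compatible with an excess of 20 points.

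**5. Chance of ruling out an excess when there is none.** Power = Φ(m/SE − 1.96), for an illustrative excess m to be excluded. With m = 10 points it is 80%, 55% and 45% at 10%, 20% and 30% mortality. With m = 5 points it is 29%, 18% and 15%.

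**6. Effect of incomplete follow-up.** With 100 evaluable per arm (an illustration), 1.96 × √(2p(1−p)/100) gives 8.3, 11.1 and 12.7 points at 10%, 20% and 30%. The figures in step 2 are therefore optimistic.

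**The case against.** The strongest reply is that the protocol never says a p-value above 0.05 will be taken as no harm. That is correct. A reader might infer that non-significance is the only support the plan allows, or that the sponsor will report a non-significant result as confirmation. Neither is in the text. Logistic and Cox models yield estimates and confidence limits as well as p-values, and a randomized comparison can bound an excess. What stands is narrower: the plan gives no criterion, so the weak reading is left open.

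A reader might also infer that arrhythmias below 250 bpm simply go untreated in the ultra-conservative arm. The documents say more than that. ICD Programming describes a symptom-driven pathway with same-day cardioversion, and the second vendor table adds VT-zone pacing therapy after symptoms that prompt external cardioversion. The exposure is less absolute than the initial settings suggest.

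Nor do the documents make an 8-point excess a planning scenario. The Study Rationale cites a case series with no deaths and rare syncope due to arrhythmia, and registry analyses with higher mortality among patients with an active ICD and treated arrhythmia. This background makes harm less expected, but it does not rule harm out or supply a criterion.

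Finally, a full non-inferiority trial may be out of reach at this size. The point does not ask for one.

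**Conclusion.** The point holds as a mismatch between the hypothesis and the design. The plan is adequately sized for shocks but has no means of supporting its no-increase claim. The numerical size depends on event rates that the documents do not give, and the 8-point excess is a yardstick rather than a forecast. Across the assumed 10% to 30% mortality range the message does not change: precision is about ±7 to ±11 points, and an 8-point excess would be missed at least half the time. For syncope at an assumed 5%, precision is about ±5 points, as large as the rate itself. No figure is offered for hospitalization, for which the documents give no rate. Only at mortality near 10%, with an excess of about 10 points accepted as tolerable, would 280 be roughly enough to support the claim. This should be settled before the 6-month and 1-year interim analyses, because a threshold set after by-arm results are known would carry little weight.

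**What to change.** - **Introduction, Objectives and Endpoints, Statistical Plan:** state that the 24-month arm differences in mortality, syncope and hospitalization will be reported with two-sided 95% CIs. Claim no increase for an outcome only if its upper limit lies below an excess that the sponsor writes down before any by-arm data are seen, including at the interim analyses. Otherwise conclude that harm is not excluded, and quote the upper limit.
- **Synopsis and Introduction:** reconcile, in the same edit, whether mortality and syncope are primary endpoints or data collected. Without this, the new wording would either contradict the synopsis or demote two listed primary endpoints without saying so.
- **Sample Size:** state the expected precision for the safety outcomes, using the sponsor's own event rates and its own allowance for transplant and loss to follow-up. The half-widths above rest on assumed rates and complete follow-up and should not be copied in.

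The cost is wording and one precision calculation, with no extra patients or data. The downside is that the trial will probably have to make a weaker safety statement than its hypothesis now promises.

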## **Study Rationale**

The current International Society for Heart and Lung Transplantation (ISHLT) guidelines provide a class I recommendation for tachy-therapy re-activation in patients with ICDs undergoing LVAD implantation [1]. However, these guidelines reflect a survival benefit observed in cohorts comprised primarily of older-generation PF LVADs [2, 3]. While the overall VA prevalence in the LVAD population exceeds 50% [4-6] with VA usually occurring >200 beats per minute [7], VA are generally well-tolerated both hemodynamically and symptomatically. Observed LVAD flows do decrease during sustained VA [8, 9], but there are multiple case reports of LVAD patients remaining awake and asymptomatic despite hours of ventricular fibrillation [10-12] and a large case series reported no deaths and rare syncope due to VA in CF LVAD patients [7]. Contrary to guidelines, contemporary evaluations restricted to CF LVADs show no clear ICD survival benefit in single center studies [7, 13] nor a large, pooled meta-analysis [14]. In fact, propensity-matched analyses of CF LVAD patients in the INTERMACS [15] and UNOS [16] registries have demonstrated increased mortality and more hospitalizations among patients with an active ICD and treated VA.

It is unclear in the CF LVAD population whether ICD shocks themselves are harmful or rather identify a higher-acuity patient subgroup. In the general HF population, however, shocks have consistently been associated with worse outcomes [17-21]. Shock reduction programming resulted in reduced mortality in the MADIT-RIT trial [22], suggesting shocks may be directly harmful and not only a marker of substrate

## **STOP SHOCK LVAD study**

05/29/2019

Pg 2

severity. In addition, repeated ICD shocks have been clearly linked to psychological harm [23-26] in the form of post-traumatic stress disorder (PTSD).

Despite signals towards physical and psychological harm, the predominant U.S. practice pattern is to maintain active ICD tachy-therapy in CF LVAD patients. In a nationwide single-vendor study, 93% of LVAD patients retained active ICDs. While only 5% were re-programmed in a strategy aimed to minimize shocks, >50% were programmed in a manner more likely to deliver tachy-therapy than in a non-LVAD, primary prevention HF population [Kiehl HFSA 2017]. This discordance triggered a small, single-center study that prospectively evaluated multiple-zone ultra-conservative ICD programming in CF LVAD patients [27]. While no reduction in shocks was observed, there was also no signal towards clinical harm. Nevertheless, by programming multiple zones for ventricular tachycardia (VT) and VF, detection rates and intervals were not fully maximized. The authors concluded that a prospective trial of a monitor-only programming strategy was needed, however this remains impossible due to vendor-locked programming restrictions. The proposed study aims to evaluate the most “ultra-conservative” VA tachy-therapy currently programmable in CF LVAD patients.

## **OBJECTIVES AND ENDPOINTS**

To evaluate the utilization of an “ultra-conservative,” single-zone programming strategy for ICD tachy-therapies in CF LVAD patients as compared to a passive strategy of standard programming (at the discretion of the provider). The study hypothesis is that an ultra-conservative strategy will result in a reduction in shocks and an improvement in quality of life without increasing adverse outcomes including death, hospitalization, and syncope among patients on CF LVAD support.

### *Sample Size*

The projected sample size is 280 enrolled subjects, 140 randomized to each programming arm. Prior observed ICD shock rates in similar CF LVAD + ICD cohorts were 21% over 11 month follow-up in a study by Richardson et al [27] and 13% over 15 month follow-up in the aforementioned internal study currently under review by Kiehl et al. We thus projected an annual ICD shock incidence of 17% (the mean of the prior 2 studies). Thus, in order to detect a 15% absolute risk reduction in shocks over 2-year follow-up with 80% power and two-tailed  $\alpha=0.05$ , 280 patients are needed.

### *Statistical Plan*

At the end of study enrollment, baseline characteristics will be compared with potential covariates of interest able to later be balanced either via multi-variable regression or propensity analysis if needed. For continuous outcomes, linear regression will be utilized, for categorical outcomes, logistic regression will be utilized, and for time to event outcomes, Cox regression will be utilized.

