**Follow Up**

	Screening Enrollment	1 mo	3 mo	6 mo	9 mo	12 mo	15 mo	18 mo	21 mo	24 mo
History, demographics, cardiac test results	x									
Informed Consent	x									
Randomization	x									
Office Visit	x		x	x		x		x		x
Research Visit *, including assessment for AE/SAE/QOL		x			x		x		x	
Device interrogation/data (may be remote)		x	x	x	x	x	x	x	x	x

*\*Can be completed in-office, by phone, medical record review and from the Interagency Registry of Mechanically Assisted Circulatory Support/NIH registry.*

*All visits follow the schedule of routine LVAD follow up.*

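### QOL is scheduled four times per patient, but the plan gives only linear regression, with no repeated-measures structure, analysis visit, per-patient summary or rule for missing scores

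*Combined protocol and SAP*

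**What the plan says.** QOL is a secondary endpoint. The Introduction states: "Secondary endpoints include time to first ICD shock, time to first VT/VF shock, and Quality Life questionnaires". The Objectives and Endpoints section makes it part of the hypothesis: the tested strategy "will result in a reduction in shocks and an improvement in quality of life". A comparison of QOL between arms is therefore implied.

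The Follow Up table places QOL in the row "Research Visit *, including assessment for AE/SAE/QOL", marked at months 1, 9, 15 and 21. The row has no mark at enrollment or at month 24. Its footnote reads: "Can be completed in-office, by phone, medical record review and from the Interagency Registry of Mechanically Assisted Circulatory Support/NIH registry".

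The Statistical Plan is one short paragraph. For a continuous score it says "For continuous outcomes, linear regression will be utilized". Logistic and Cox regression are named for categorical and time-to-event outcomes. The only other provision is that covariates may be "balanced either via multi-variable regression or propensity analysis if needed", which does not deal with correlation between scores from the same patient. No QOL instrument, analysis visit, summary measure or missing-score rule appears anywhere in the document.

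**The concern.** Up to four scores from one patient are correlated. A single linear regression does not say what to do with them. Taking one visit sets the others aside and drops every patient without a score at that visit, even when that patient's other scores are usable. Pooling all scores as if each came from a different patient makes the standard error too small. Because the choice is open and the trial is unblinded (Randomization section), an analyst could settle on a visit, a summary or a pooled analysis after seeing the data.

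The footnote adds to this. A visit that carries QOL may be completed from records alone, and unless those records hold a questionnaire the patient filled in, that visit yields no score. Death also ends a patient's scores, so a mean among survivors can favour the arm with more deaths. Since QOL improvement is one of the two benefits hypothesised, the result could be less precise than it need be or, under pooling, falsely significant.

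**Working it through.** **The plan's own figure.** No figure is given for QOL. The one design figure belongs to the shock endpoint: "The projected sample size is 280 enrolled subjects, 140 randomized to each programming arm". It is approximately reproducible. An annual incidence of 17% compounds to 1 − 0.83² = 31.1% at two years. Against 16.1%, with two-sided 0.05, 80% power and a continuity correction, 138 per arm are needed, or 276 in all. The plan does not state which formula it used. Only the 140 per arm is carried forward.

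**Inputs**
- Scheduled scores per patient: m = 4 (Follow Up table).
- Patients per arm: 140 (Sample Size).
- Within-patient correlation ρ: not in the documents. Assumed 0.5, range 0.3 to 0.7, equal for every pair of visits.
- Also assumed: complete data and equal variance at each visit, with differences in standard deviation (SD) units.

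**Step 1: all scores pooled as independent** (280 × 4 = 1,120 scores). True SE divided by reported SE = √(1 + 3ρ). Actual type I error = 2 × [1 − Φ(1.96 / ratio)].

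| ρ | SE ratio | Type I error, formula | Simulated |
|---|---|---|---|
| 0.3 | √1.9 = 1.38 | 15.5% | 15.5% |
| 0.5 | √2.5 = 1.58 | 21.5% | 21.6% |
| 0.7 | √3.1 = 1.76 | 26.6% | 27.0% |

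The simulations used 20,000 replicates. In the same runs, regression on each patient's four-visit mean rejected in 5.0%, 4.7% and 5.2% of replicates. Linear regression can therefore use all the scores and keep its level.

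**Step 2: one visit against the average of four.** The variance of the four-visit mean relative to one visit is (1 + 3ρ)/4, so the one-visit interval is wider by the factor √(4/(1 + 3ρ)). The difference detectable with 80% power from one visit is (1.96 + 0.84) × √(2/140) = 0.335 SD. For four visits this is multiplied by √((1 + 3ρ)/4).

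| ρ | One-visit interval wider by | Detectable, four visits |
|---|---|---|
| 0.3 | √(4/1.9) = 1.45, 45% | 0.231 SD |
| 0.5 | √(4/2.5) = 1.26, 26% | 0.265 SD |
| 0.7 | √(4/3.1) = 1.14, 14% | 0.295 SD |

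**Step 3: which visits to average.** The ICD Programming section allows reprogramming at clinic follow-up up to 30 days, so month 1 may show little effect. Suppose the effect is zero at month 1 and constant afterwards. The four-visit average then carries 75% of it. Its signal-to-SE ratio, relative to one late visit, is 0.75 / √((1 + 3ρ)/4) = 1.09, 0.95 and 0.85 at ρ = 0.3, 0.5 and 0.7. The average over months 9, 15 and 21 has relative variance (1 + 2ρ)/3 and no dilution, so its ratio is √(3/(1 + 2ρ)) = 1.37, 1.22 and 1.12. Under this pattern the three later visits beat a single visit throughout the range. The four-visit average does so only at the low end.

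**The case against.** A reader might infer that linear regression forces a choice between ignoring correlation and discarding data. It does not. Regression on a per-patient mean, area under the curve or slope, or with cluster-robust errors, does neither. This stands. The plan specifies none of these, however, and with gaps in the scores a simple per-patient mean would average different visits for different patients.

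A reader might also infer that the trial will report a QOL result with about 21.5% type I error. No section says the scores will be pooled, so that figure is conditional on an analysis the plan does not describe.

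Nor does using one visit lose three quarters of the information. Three quarters is the share of scores. With (1 + 3ρ)/4 of the information on the average difference kept, the loss is 22.5% at ρ = 0.7 and 52.5% at ρ = 0.3. A single late visit is also a legitimate target, and with complete data a repeated-measures model gains essentially nothing at that one visit. Its gain comes from averaging visits and from using patients with partial scores. As Step 3 shows, an average that includes month 1 can be weaker than one late visit, so the choice of contrast matters.

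Three further reservations stand. The instrument is unnamed, so a continuous score is itself an assumption. The documents do not say whether the records or the registry hold patient-completed QOL, and the footnote also allows office and phone completion, so gaps are possible rather than shown. A mixed model does not cure truncation by death.

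**Conclusion.** The point holds as a gap in specification. Four scores are scheduled, the only method that could apply to a continuous score is linear regression, and no other section supplies a repeated-measures method, an analysis visit, a summary or a missing-score rule. If one visit were used, the interval for the average arm difference would be about 26% wider than with four visits (14% to 45%). If all scores were pooled without allowance for correlation, type I error would be about 21.5% (15.5% to 26.6%). Both figures rest on an assumed within-patient correlation of 0.3 to 0.7, equal between visits, and on complete data. The documents do not support saying that the plan will pool scores or that a false QOL finding is to be expected. The point concerns a secondary endpoint that carries part of the hypothesis. The primary shock analysis and the 280 patients are unaffected.

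**What to change.** In the Statistical Plan, if the QOL score is continuous, replace linear regression for QOL with a mixed model for repeated measures: arm, visit, arm-by-visit interaction and an unstructured within-patient covariance. Pre-specify one contrast, for example the average arm difference over months 9, 15 and 21, since month 1 may fall at or near reprogramming. Report deaths and transplants by arm beside the QOL result, and state that the model does not remove bias from truncation by death.

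In the Follow Up table, require a patient-completed QOL form (paper, phone or online) at these visits, so that record review alone does not count as a QOL assessment.

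The cost is a few sentences, standard software, and a small number of extra phone or online questionnaires at visits that would otherwise be done from records.

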## **Randomization**

Randomization to ultra-conservative versus standard programming will occur at the time of study enrollment using REDCap. Randomization will be a 1:1 ratio. Neither the patient nor treatment team are blinded to the randomization or programming assignment. ICD re-programming will occur in the device clinic or patient hospital room as per the current routine care pathway.

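### No test or sparse-data rule is given for low-count binary outcomes; if the control arm has no syncope, routine logistic output cannot show harm.

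*Combined protocol and SAP*

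**What the plan says.** The Statistical Plan section assigns one method to each outcome type. For yes/no outcomes it says "for categorical outcomes, logistic regression will be utilized"; for event times, "for time to event outcomes, Cox regression will be utilized". It allows covariate balancing by multivariable regression or propensity analysis if needed. It names no test statistic, no interval method and no rule for sparse or empty cells.

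Syncope is not named in that section. The synopsis lists it under primary endpoints ("Any ICD shock Mortality Syncope"), while the Introduction treats it as collected data ("Data collected will include mortality, syncope, LVAD-related hospitalizations (including HF, VA"). Objectives and Endpoints puts it in the hypothesis: fewer shocks "without increasing adverse outcomes including death, hospitalization, and syncope among patients on CF LVAD support". The only time-to-event endpoints listed are time to first shock and time to first VT/VF shock, so syncope falls under logistic regression by elimination.

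On frequency, the Study Rationale says only that "a large case series reported no deaths and rare syncope due to VA in CF LVAD patients". On size, "The projected sample size is 280 enrolled subjects, 140 randomized to each programming arm".

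**The concern.** Logistic regression relies on large-sample theory that fails when one arm has no events. The maximum-likelihood log odds ratio then runs to infinity, its standard error grows without limit, and the Wald p-value printed beside the coefficient approaches 1 however many events the other arm has. Adding covariates to a model with few events makes the fit less stable still.

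The direction matters. The pattern a safety analysis should catch is no syncope under physician-directed programming and several cases under ultra-conservative programming. In that case the default output would look like an absence of difference, for an outcome on which the trial hopes to report no increase. The planned looks at 6 months and 1 year would have fewer events than the final analysis.

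**Working it through.** **Inputs.** 140 per arm (Sample Size), 1:1 allocation (Randomization). Two-sided 0.05 is stated for shocks and is applied here to syncope by assumption. No syncope rate is given, so control risks of 0.5% to 5% over 2 years are assumed. No dropout is applied, because none is stated.

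**The plan's own figure.** The only stated calculation is 280 patients for shocks. Taking 2 × 17% = 34% against 19%, the pooled two-proportion formula gives 270 in total, and 140 per arm has 81.5% power. The figure is reproduced well enough, but it says nothing about syncope.

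**Step 1: chance of an empty control arm.** P(no events) = (1 − p)^140.

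| Assumed control risk | P(no control events) |
|---|---|
| 0.5% | 0.995^140 = 50% |
| 1% | 0.99^140 = 24% |
| 2% | 0.98^140 = 6% |
| 3% | 0.97^140 = 1.4% |
| 5% | 0.95^140 = 0.1% |

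**Step 2: one worked table, 0/140 control against 6/140 ultra-conservative.**

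- Wald: no finite log odds ratio. After 25 iterations the fit stands at 23.5 with a standard error of about 30,000, so z is about 0.001 and p about 0.999. The standard error depends on where the software stops; the p-value conclusion does not. Wald p is also 0.999 at 0 against 20.
- Score: pooled risk 6/280 = 0.0214; SE = √(2 × 0.0214 × 0.9786 / 140) = 0.0173; z = 0.0429 / 0.0173 = 2.48; p = 0.013.
- Likelihood ratio: 2 × [6 ln(6/140) + 134 ln(134/140) − 6 ln(6/280) − 274 ln(274/280)] = 8.45; p = 0.004.
- Fisher exact: p = 0.030.
- Firth-penalised logistic: odds ratio 13.6, profile 95% interval 1.58 to about 1,777, p = 0.013.
- Miettinen-Nurminen 95% interval for the risk difference: lower limit just above 1.5 percentage points, upper limit about 9.0.

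**Step 3: power.** Rejection probabilities were summed over the two binomial distributions (n = 140 each). Wald was counted as non-significant when either arm was empty.

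| Control vs ultra-conservative | Wald | Score | Fisher |
|---|---|---|---|
| 0.5% vs 6% | 27.5% | 80.7% | 67.8% |
| 1% vs 6% | 35.4% | 65.1% | 51.8% |
| 2% vs 6% | 28.9% | 39.5% | 27.8% |
| 3% vs 6% | 17.6% | 21.9% | 13.8% |
| 5% vs 10% | 33.7% | 34.5% | 27.3% |
| 1% vs 3% | 2.8% | 20.2% | 8.4% |

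**Step 4: size with equal risks.** The score test's two-sided size was at most 4.8% at common risks of 0.5%, 1%, 2%, 3% and 5%. The likelihood-ratio test's size was 8.3% at 1% and 8.8% at 2%.

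**The case against.** The strongest reply is that the plan never names a Wald test. A reader might infer that the planned test is one that cannot show harm, but the section says only that logistic regression will be used. The same model yields likelihood-ratio and score tests that do detect 0 against 6. That stands: the gap is an unspecified test and a missing sparse-data rule, and logistic regression as such is usable. The likelihood-ratio test is not a clean rescue, though, because its size reaches 8% to 9% at 1% to 2% risk. Picking a test after seeing an empty arm in an unblinded trial would also be open to challenge.

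A second tempting reading is that the protocol expects syncope to be rare. It does not say so. The Study Rationale describes syncope caused by ventricular arrhythmia in one cited case series, whereas the endpoint has no cause restriction and no stated rate. If syncope of any cause runs at 5% or more, an empty arm is very unlikely and the choice between Wald and score hardly matters. That stands too, and is why the full range is shown.

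Third, a huge standard error and a raw count of 0 against 6 are hard to miss, so a careful analyst might not report p = 0.999 as reassurance. That is fair, but pre-specification removes the need to rely on it. Analysing syncope by Cox regression would not help: the hazard ratio also has no finite estimate when one arm has no events.

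Finally, a rise to 6% is 12-fold, 6-fold, 3-fold or 2-fold from 0.5%, 1%, 2% or 3%. For 1% against 3%, score power is only 20%, so a better test does not make an absence of increase demonstrable.

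**Conclusion.** The point holds as a gap in specification. The plan gives every categorical outcome one model, without a test or a sparse-data rule, and by inference this covers a safety outcome that may have few events. If the control arm is empty, the odds ratio is not estimable and the default coefficient-table p-value cannot show harm.

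The consequence depends on a syncope rate that the documents do not give. At assumed control risks of 0.5% to 2% the loss of power against a rise to 6% is between about 11 percentage points (28.9% against 39.5%, from 2%) and 53 percentage points (27.5% against 80.7%, from 0.5%). At 3% it is about 4 points, and at 5% against 10% about 1 point. Harm is masked in this way only when the empty arm is the control arm.

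The documents do not support saying that a Wald test is planned, that syncope is expected to be rare, or that changing the test would make the trial adequate for syncope. This is a cheap improvement.

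**What to change.** Add one or two sentences to the Statistical Plan. Syncope and other binary outcomes with few events, such as inappropriate shocks, are reported as a between-arm risk difference with a Miettinen-Nurminen 95% confidence interval and the matching score test. If covariate adjustment is wanted, use Firth-penalised logistic regression with profile-likelihood intervals. Ordinary logistic regression stays for outcomes with enough events, and the event count that separates the two should be fixed in advance.

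Fisher's exact test is not the recommended substitute: at 2% against 6% it has slightly less power than Wald, and at 3% against 6% and 5% against 10% it falls further behind.

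The plan should also say that any statement about an increase in syncope rests on the confidence interval and not on a non-significant p-value.

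The cost is the added text. No new data or visits are needed, and where syncope proves common the score test gives up nothing in the cases run. The downside is little or no covariate adjustment for these outcomes.
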